8.2.2. Reports for which this Statistical Analysis Plan applies

This Analysis plan shall apply to the final report. The plan will also be used for the interim analysis at the end of Phase I data collection. Statistical analysis for study related publications will not be limited to this plan.

8.3. Demographic and Other Baseline Characteristics

8.3.1. Description of Baseline Variables

A number of characteristics will be reported for each enrolled subject on baseline case report forms (CRFs) at time of enrollment. The variables collected will include demographics, medical history, symptoms, vitals, and cardiovascular medications. Tables and descriptive statistics will be used to summarize subject data with respect to these variables. For quantitative variables such as age, the mean, standard deviation, median, the first quartile and third quartile, minimum and maximum will be presented. For qualitative variables, counts and percentages will be given.

8.4. General Summaries

The Medtronic statistician who is assigned to the project will conduct all statistical analysis. Sample size package PASS 2008 was used for sample size evaluation. The two primary endpoints are the change in the proportion of subjects with an SND diagnosis after intervention and the change in the proportion of subjects receiving IPG therapy after intervention. In current practice, both of these proportions are unknown for a set of subjects meeting the study inclusion criteria. Three principles will guide the statistical analysis outlined below. The first principle is that the sample size calculations will use exact confidence intervals and tests to compare binomial proportions. The second principle of the analysis is that sample size calculations for Phase II of the study design will depend on the outcomes observed in Phase I of the study design. Due to this, the Phase II sample size calculations provided herein are preliminary calculations that will be amended once Phase I data collection is completed. In general the study will start with a 1:2 collection ratio for Phase I and Phase II sample sizes. Twice as many subjects are enrolled in Phase II of the study design so that the study may also examine any temporal drift in the outcomes of interest or subject demographics. The third principle of the analysis is that both the

This document is electronically controlled. Printed copies are considered uncontrolled.

Confidential

statistical methods and the sample size calculations will be geography specific because the study outcomes are expected to vary by geography.

8.5. Evaluation of Objectives

8.5.1. Primary Objective #1

Evaluate the impact of the intervention on the diagnosis of SND.

8.5.1.1. Analysis Methods

A. Statistical Methodology

To compare the proportion of subjects with an SND diagnosis pre-intervention (Phase I) to the proportion post-intervention (Phase II), a chi-square test will determine statistical significance. The proportion of subjects diagnosed will be evaluated at multiple time points because the time to diagnosis is expected to vary by geography. Thus, times are pre-specified starting at 6 months and any additional 6-month interval thereafter for which there is sufficient follow-up data available to compare study phases.

Proportions calculated at all available time points will be reported. Additionally a Poisson regression will compare the average number of subjects with an SND diagnosis in Phase I and Phase II where the subject time in study is treated as an offset in the model. The above described tests will be performed only for subjects in the South Asia geographical region as per section 6.

[REDACTED]

[REDACTED]

This document is electronically controlled. Printed copies are considered uncontrolled.

Confidential

[REDACTED]

[REDACTED]

[REDACTED]

B. Determination of Patients/Data for Analysis

All subjects that are enrolled in the study will be included in the determination of the proportion estimates. The proportion estimates will be calculated based on information from fixed time points at 6 months of follow-up, 12 months of follow-up, and any additional 6-month interval thereafter for which there is sufficient follow-up data available to compare study phases. The number of subjects that obtain an SND diagnosis by pre-specified time point $t = 6, 12, \text{ etc.}$, is included in the numerator and the number of subjects enrolled is included in the denominator.

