4.3 Study Design

There are two phases to IMPROVE Brady:

Phase I: This phase of the study serves as a control period. During Phase I physicians will assess and treat subjects per their site's standard care practice. Enrollment for Phase I is anticipated to occur for approximately 12 months but will continue until 550 subjects have been enrolled for the geography/country. For subjects enrolled during Phase I, collection of diagnostic assessment and implant data will be complete 6 months after the last enrollment for the geography/country. At that time, all Phase I subjects will be exited.

If a center becomes active after the geography/country enrollment goal for Phase I has been met or the center did not enroll at least 10 subjects before Phase I enrollment stopped then the center will enroll Phase I subjects until 10 subjects have been enrolled at that center. Once 10 subjects have been enrolled at the center, enrollment will stop and the subjects will be followed for a maximum of 6 months and exited from the study.

Phase II:

The objective of the IMPROVE Brady study is to provide investigators with comprehensive resources that may be adapted by the Principal Investigator and his/her colleagues to create a practice specific process improvement intervention to improve the quality of care for patients.

At the completion of Phase I, the Principal Investigator and co-investigators will complete an educational workshop and be given access to the IMPROVE Brady toolkit. In addition, the Principal Investigator and his/her colleagues are encouraged to adapt tools from the IMPROVE Brady toolkit to create a practice specific process improvement intervention.

Immediately following completion of the educational workshop, study investigators will receive written authorization from Medtronic that they are authorized to enroll subjects in Phase II. Enrollment during this phase is anticipated to occur for approximately 18 months per geography/country.

[figure not shown]
The IMPROVE Brady process improvement intervention toolkit may include an education workshop, diagnostic algorithm(s), patient video and tools for investigators to educate their patients on their disease state, available therapy options, and benefits and risks associated with the therapy options.

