4.4 Minimization of Bias

Potential sources of bias in this study may result from the Hawthorne effect, selection of study centers, selection of subjects, treatment of subjects, and evaluation of study data. The following methods have been incorporated into the study to minimize potential bias.

- Center selection criteria, documented under separate cover, will need to be met prior to participation in IMPROVE Brady
- Study center characteristics will be collected at activation on possible differences that may effect the primary endpoints
- Centers will be used as their own control
- Subjects will be screened to confirm eligibility for enrollment with defined inclusion/exclusion criteria prior to enrollment
- Subject demographics will be collected at baseline on possible differences that may effect the primary endpoints
- It is anticipated that the distribution of subjects with various co-morbidities will vary by study centers. To minimize potential bias, all sites will be encouraged to enroll at least 10 subjects in each study Phase and enrollment at a site cannot exceed 20% of the sample size for the geography/country to ensure a more even distribution of data
- All study Clinicians will be required to follow the Clinical Investigation Plan
- All study clinicians and Medtronic personnel will be trained on their respective aspects of the clinical investigation plan using standardized training materials.

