4.2.5.1. Endpoint Definition

Compare the difference in QOL and functional status between pre-implant and 6 months post-implant. The composite physical and mental scores from Version 2 of the SF-12 Health Survey will be used to assess QOL.

[REDACTED]

[REDACTED] [REDACTED]

[REDACTED]

[REDACTED]

[REDACTED]

[REDACTED] [REDACTED]

[REDACTED]

This document is electronically controlled. Printed copies are considered uncontrolled.

Confidential

[REDACTED]

[REDACTED]

[REDACTED]

[REDACTED]

[REDACTED]

[REDACTED]

5. Investigation Plan

Study Design Overview

The study may be conducted in countries located in Central and Eastern Europe (CEE), Greater China, India, Latin America, Asia, and Middle East and Africa (MEA). Countries from other geographies may be added in the future. The distribution of centers will be approximately 10 per geography or country and is determined by local evidence needs.

Approximately 1,650 subjects per geography/country, or up to 14,850 subjects worldwide, will be enrolled in the study. An enrollment target of 6 subjects per center per month is desired to make center-specific outcomes more meaningful and reliable in measuring changes in diagnostic rates and patient acceptance of indicated therapy. Centers that enroll faster than others will be allowed to enroll until 20% of the sample size for the geography/country has been reached for a maximum of 330 subjects per site - 110 maximum in Phase I and 220 maximum in Phase II.

All study subjects will be followed until the study exit criteria are met or until official study closure. Study closure is defined as closure of a clinical study that occurs when Medtronic and/or regulatory requirements have been satisfied per the Clinical Investigation Plan and/or by a decision by Medtronic or regulatory authority, whichever occurs first. The expected study duration per geography/country, from first enrollment to last follow-up, is approximately 4.5 years per geography/country.

Subjects will have successfully completed the study if one of the following criteria has been met:

1. Subject does not meet a class I or class II SND indication for pacing therapy
2. Subject meets an indication for pacing but not an SND indication for pacing therapy
3. Subject has met an SND indication for pacing therapy and did not receive a market released pacemaker from the Medtronic family of devices
4. Subject has met an SND indication for pacing therapy but will not be receiving pacing therapy

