8.2. General Methodology

8.2.1. Special Considerations

The study will have an enrollment restriction. The maximum number of subjects to be enrolled at any given study center is 20% of the expected sample size in that geography; 20% of 1650 subjects equals 330 subjects per study center.

Sample size calculations will account for an attrition rate in the study of 10%.

An analysis will be built to examine temporal confounding. Since the study design does not randomize the treatment and control subjects it is possible that the time elapsed over Phase I and Phase II of the study will confound the results. To examine the possibility of temporal confounding, an interrupted time series regression analysis will be performed. This analysis will adapt Rubin's causal model for rate parameters.

This document is electronically controlled. Printed copies are considered uncontrolled.

Confidential

Rubin's causal model for linear outcome Y is $Y = \beta_0 + \beta_1 X + \beta_2 D$, where X is time and D is a dummy variable for group assignment, before and after intervention. To adopt this model for rate parameters estimated in the primary objectives of the study, the model to be fit is $\log(Y) = \beta_0 + \beta_1 X + \beta_2 D + \log(Z)$ where Y is a binary response to indicate an SND diagnosis and Z is the amount of subject follow-up. The same model will also be fit to model the rate of IPG treatment. If an association is seen by testing β_1 , then temporal confounding exists.

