8.5.2.1. Analysis Methods

A. Statistical Methodology

To compare the proportion of subjects that receive indicated therapy pre-intervention (Phase I) to the proportion post-intervention (Phase II), a Fisher's Exact test will determine statistical significance. A Fisher's exact test is recommended for smaller sample sizes. The proportion of subjects diagnosed will be evaluated at multiple time points because the time from diagnosis to implant is expected to vary by geography. Shorter time intervals will be used to evaluate the proportion of implants than for the proportion of diagnosis because time from diagnosis to implant is typically shorter than the time from enrollment to SND diagnosis. Thus, times are pre-specified starting at 3 months and any additional 3-month interval thereafter for which there is sufficient follow-up data available to compare study phases. Proportions calculated at all available time points will be reported. Additionally, a Poisson regression will compare the average number of subjects with an implant where the subject time in study beginning at the time of SND diagnosis is treated as an offset in the model. The above described tests will be performed only for the South Asia geography as described in Section 6. Further, similar tests will compare the differences in the types of therapy received in Phase I and Phase II. For example, a Fisher's exact test will compare the frequency of dual chamber device use pre- and post-intervention.

This document is electronically controlled. Printed copies are considered uncontrolled.

Confidential

B. Determination of Patients/Data for Analysis

Subjects that meet inclusion criteria and obtain an SND diagnosis shall be included in this analysis. The proportion estimates will be calculated based on information from fixed time points at 3 months of follow-up, 6 months of follow-up, and any additional 3-month interval thereafter for which there is sufficient follow-up data available to compare study phases. The number of subjects that obtain an IPG by pre-specified time point $t = 3, 6, \text{ etc.}$, will be included in the numerator and the number of subjects with an SND diagnosis will be included in the denominator.

C. Additional Analyses

- In addition to the overall diagnosis and treatment rates between Phase I and Phase II, various descriptive summaries of the subjects will be explored by geography, including the following:

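### Centers are declared their own control, but no readable primary analysis stratifies by or adjusts for site, so a change in site mix between phases can look like an intervention effect or hide one

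*SAP*

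**What the plan says.** Protocol 4.4 (Minimization of Bias) names differences between centers as a source of bias, expects co-morbidities to vary by center, and states that "Centers will be used as their own control".

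The primary analyses in the SAP are:
- **Objective 1 (8.5.1.1):** "a chi-square test will determine statistical significance", plus a Poisson regression on phase with time in study as offset.
- **Objective 2 (8.5.2.1):** "a Fisher's Exact test will determine statistical significance", plus a Poisson regression with time since diagnosis as offset.
- **Temporal confounding (8.2.1):** "an interrupted time series regression analysis will be performed". Its model has an intercept, time, a phase indicator and log follow-up.

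None of these names site as stratum, covariate or cluster. Protocol 11.1, which has no redactions in its primary analysis text, has none either. SAP 6 limits phase comparisons to South Asia. It restricts by-site analyses to sites active in both phases, but does not extend that rule to the primary tests, which use all enrolled subjects.

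The enrollment rules let site shares move. A center that activates late, or has fewer than 10 subjects when Phase I closes, is handled as follows: "then the center will enroll Phase I subjects until 10 subjects have been enrolled at that center" (Protocol 4.3). For Phase II, "Enrollment during this phase is anticipated to occur for approximately 18 months per geography/country". SAP 5 adds: "An enrollment target of 6 subjects per center per month is desired", and lets a fast center continue "for a maximum of 330 subjects per site - 110 maximum in Phase I and 220 maximum in Phase II".

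Protocol 11.2 stratified the log-rank tests for Secondary Objectives 2 and 3 by geography/country and by site. The readable SAP text for these tests (8.5.4.1 and 8.5.5.1) no longer mentions site strata.

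**The concern.** In a non-randomized before/after study, site is a foreseeable confounder, and one that the design can remove, because Protocol 4.3 has every center enroll Phase I subjects before it enters Phase II. The protection comes only from an analysis that compares each center with itself. A pooled 2×2 table does not do that.

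If centers with high diagnosis or implant rates supply more of Phase II than of Phase I, the pooled proportion rises although no center has changed. If they supply less, a real improvement is diluted. The direction depends on which centers grow, so it cannot be assumed conservative. At stake is whether a significant result, or its absence, can be read as the effect of the workshop and toolkit.

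**Working it through.** **1. The plan's own figure.** SAP Table 2 gives 593 Phase II subjects for 20% against 30% (90% power, alpha 0.05, 2:1). With p̄ = (0.20 + 2×0.30)/3 = 0.2667:

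n₁ = [1.960·√(3·0.2667·0.7333) + 1.2816·√(2·0.20·0.80 + 0.30·0.70)]² / (2·0.10²) = (1.501 + 0.933)² / 0.02 = 296.3

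n₂ = 2n₁ = 592.5, rounded up to 593. The figure reproduces with a two-sided test and no site term, so the sample size treats each phase as one homogeneous group.

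**2. How site mix enters.** If no site changes, the expected pooled difference is the sum over sites of (Phase II share − Phase I share) × site rate. For a group of high-rate sites this is (change in their share) × (their excess rate).

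**3. What the enrollment rules permit.** A late-activated center stops Phase I at 10. At the target pace it then adds 6 × 18 = 108 in Phase II. If Phase II closes on a common date, 108 is an upper figure, because the center must first enroll its 10 subjects and follow them for up to 6 months. A slow center is different. Fewer than 10 in about 12 months is under 10/12 = 0.83 per month, hence under 15 in 18 months at an unchanged pace.

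**4. Worked case, Objective 1.** Assumed: 550 Phase I subjects at eight sites, plus two late sites with 10 each on top; 1,100 in Phase II, of whom the two late sites supply 216; late sites at 30%, all others at 20%, no change at any site.
- Phase I: 0.20 + 0.10×20/570 = 0.2035
- Phase II: 0.20 + 0.10×216/1100 = 0.2196
- SE = √[0.2141×0.7859×(1/570 + 1/1100)] = 0.0212, so expected z = 0.0161/0.0212 = 0.76
- Rejection = Φ(0.76 − 1.96) + Φ(−0.76 − 1.96) ≈ 0.12

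With late sites at 40% the rates are 0.2070 and 0.2393, expected z is 1.49, and rejection is 0.32.

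**5. Range, by simulation.** Ten sites, no change within any site, two-sided 0.05, no continuity correction. Late sites are on top of the 550, as above.

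| High-rate sites (Phase I then Phase II, each) | Pooled rejection, sites at 25 / 30 / 40% |
|---|---|
| Two, stable shares (110 then 220) | about 5 / 5 / 5% |
| Two slow sites that stay slow (10 then 15) | 5 / 5 / 5% |
| Two, 55 then 150 | 5 / 6 / 9% |
| One late (10 then 108) | 5 / 7 / 11% |
| Two late (10 then 108) | 7 / 12 / 32% |
| Two, 55 then 220 | 7 / 14 / 40% |

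The site-stratified Cochran-Mantel-Haenszel test stays at about 5% in every row.

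**6. Masking.** Assume a true rise of 8 points at every site, with two high-rate sites at 110 then 110 (550 and 1,100 in total). With those sites at 30%, the pooled rates are 0.20 + 0.10×220/550 = 0.24 and 0.28 + 0.10×220/1100 = 0.30. The apparent rise is 6 points, pooled power is 0.73, and stratified power is 0.92. With those sites at 40%, the rates are 0.28 and 0.32, and pooled power is 0.38 against about 0.92 stratified.

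**7. Objective 2.** Take 100 and 200 SND subjects, other sites at 10% implanted, and two sites at 20 / 25 / 40%. Fisher's test rejects in 4 / 5 / 7% when those sites go from 10 to 30 SND subjects each, and in 9 / 14 / 45% when they go from 5 to 40. The exact conditional stratified test stays at about 4%.

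**The case against.** - **Redaction.** Text is blacked out directly after the primary tests in SAP 8.5.1.1 and after the log-rank sentence in 8.5.4.1. SAP 6 sets a rule for by-site analyses that no readable section defines beyond an optional look in SAP 5. Site handling may sit in the hidden text. This stands, and confirming that it does would be a sufficient answer.
- **Meaning of own control.** The phrase may only describe the before/after design, and SAP 5 ties the monthly target to reliable center-specific outcomes. That shows an intent to look within centers, but no readable primary test carries it out.
- **Design limits.** The 20% cap and the encouraged minimum of 10 per phase limit one center's dominance. They still allow 10 then 220, so they do not fix the mix.
- **Assumed alignment.** The larger figures need two high-rate centers growing together. With one high and one low late center (25/15% or 30/10%), rejection is 5%. This stands.
- **Exploratory label.** SAP 4.1 specifies no hypotheses for the primary objectives. That softens the consequence, but the tests are still said to determine significance.

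A reader might also infer that any slow center will swell to 108 in Phase II. The documents do not support that: a center below one subject per month would need roughly a sevenfold rise in pace.

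**Conclusion.** The point holds as a gap between a stated safeguard and the readable analysis. It is worth correcting, with medium confidence. With no change in any center, the pooled Objective 1 test rejects at 5 to 11% for one late high-rate center, 7 to 32% for two, and 5 to 9% for a milder shift at two centers. It shows no inflation when shares are stable or slow centers stay slow. These figures rest on 10 sites, high-rate sites 5 to 20 points above a common 20%, and the target enrollment pace. The documents give no site rates or site shares by phase.

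Two stronger readings should be resisted. One is that the trial's result is in fact biased by site mix. The documents show only that the readable plan would not prevent this, and they do not say whether shares moved or whether any center enrolled in Phase I only. The other is that the SAP has no site-adjusted analysis at all, which the redactions leave open.

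**What to change.** 1. In SAP 8.5.1.1 and 8.5.2.1, make the Phase I against Phase II test site-stratified: Cochran-Mantel-Haenszel for Objective 1 and the exact conditional stratified test for Objective 2. Add site as a factor in both Poisson regressions and in the 8.2.1 model. If redacted text already does this, say so.
2. Keep the pooled all-enrolled table as descriptive, and report counts by site and phase.
3. Restore, or confirm, the Protocol's site-stratified log-rank for Secondary Objectives 2 and 3 (SAP 8.5.4.1 and 8.5.5.1).

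No separate change to the enrolled set is needed, because a site active in only one phase carries no weight in a stratified test. A site-level paired comparison for Objective 1 is optional. It would address centers that change by different amounts between phases, which stratification does not correct.

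**Cost.** The change is to SAP wording and programming, since the enrolling site is known for each subject. Objective 1 power for 20% against 28% (500 and 1,000 subjects, 10 equal sites) is 0.93 pooled and 0.93 stratified. Under severe imbalance (two sites at 10 then 220, of 550 and 1,100) it falls from 0.95 to 0.91. Objective 2 power for 10% against 26% (100 and 200) is 0.92 with either test at equal sites. With two sites at 2 then 40 SND subjects each, it falls from 0.92 to 0.88.

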8.5.1.2. Sample Size Methods and Assumptions

The proportion of SND diagnoses in bradycardia subjects is currently unknown within the study geographies. The PANARM HF study of 2000 subjects found that 146 out of 331 bradycardia subjects (44%) had symptomatic SND and that 15 (10%) of SND subjects opted for IPG therapy (internal data on file). The power calculations conservatively assume that the SND diagnosis will be 20% at six months of follow-up, or equivalently an SND incidence of 0.4 diagnoses per person-year. Thus, the margin of error will be $\pm 4\%$ in a sample of 500 subjects per geography/country, based on a 95% confidence interval. If 500 subjects are collected in Phase I and 1000 subjects are collected in Phase II, assuming a type I error of 0.05 and power of 0.90, a chi-square test will detect an increase in SND diagnosis of at least 8%. For example, the study will find a statistically significant difference between a Phase I SND percentage of 20% at 6 months and a Phase II SND percentage of 28% at 6 months. The Poisson regression for the same scenario has a power of 0.95 to compare SND incidence of 0.4 versus 0.56 diagnoses per person-year. If the proportion of SND diagnoses is smaller than 20%, there will be more power to detect significant differences in the diagnosis proportion. Thus, the Phase II sample size will be recalculated within geography/country once Phase I data collection is complete. It is expected that the study attrition rate may be 10-15% of the study population. To account for attrition, *the sample size for Phase I will be 550 subjects per geography/country and for Phase II may be 1100 subjects per geography/country.*

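### The Poisson models for both primary objectives and for temporal confounding need a stated robust variance and a stated end to time in study; the default Poisson variance is generally not valid for a yes/no outcome

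*SAP*

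**What the plan says.** SAP 8.5.1.1 adds a Poisson regression to the chi-square test for Primary Objective #1: "Additionally a Poisson regression will compare the average number of subjects with an SND diagnosis in Phase I and Phase II". The offset in that model is each subject's time in study. SAP 8.5.2.1 adds one to Fisher's exact test for Primary Objective #2: "a Poisson regression will compare the average number of subjects with an implant where the subject time in study" runs from the SND diagnosis. The temporal-confounding model in SAP 8.2.1 is log-linear with offset log(Z), "where Y is a binary response to indicate an SND diagnosis and Z is the amount of subject follow-up". Its time coefficient, beta1, is tested to decide whether temporal confounding exists.

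The change per person-year is part of both primary endpoint definitions (SAP 4.1.1.1 and 4.1.2.1), and these regressions are its only readable test. No readable passage mentions a robust variance, a dispersion scale or a binomial model. The text straight after the Poisson description in 8.5.1.1 is redacted. Neither document says whether time in study stops at diagnosis or at implant.

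**The concern.** A subject can be diagnosed or implanted at most once in these analyses, so the outcome is 0 or 1. If every subject contributes full follow-up whatever the outcome, the variance of that outcome is p(1-p), but a Poisson model takes it to be p. The difference is negligible for rare events. These events are not rare: the plan assumes 20% and 28% for SND, cites 44% from an earlier study, and tabulates SND proportions from 10% to 95% and implant proportions from 5% to 100% (SAP section 7, Tables 2 to 4).

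At stake are the confidence intervals and tests for the per-person-year half of each primary endpoint, and the beta1 test. The design is sequential and unrandomised, so beta1 is the main guard against reading calendar drift as an intervention effect. A test that rejects too rarely makes drift easier to miss.

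**Working it through.** **Inputs (SAP 8.5.1.2 and 8.5.2.2).** For objective 1: "If 500 subjects are collected in Phase I and 1000 subjects are collected in Phase II"; "the SND diagnosis will be 20% at six months of follow-up" in Phase I and 28% in Phase II. For objective 2: 100 and 200 SND subjects, 10% v 26% at three months. Alpha is 0.05. The SAP does not state sidedness; two-sided is assumed here.

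**The plan's own power figures.** The chi-square statement ("assuming a type I error of 0.05 and power of 0.90, a chi-square test will detect" an increase of 8 points) checks out: power for 20% v 28% is 0.93. The Poisson statement ("The Poisson regression for the same scenario has a power of 0.95 to compare SND incidence of 0.4 versus 0.56 diagnoses per person-year") does not reproduce with six months' exposure and a two-sided test:
- Expected events are 100 and 280, so the Poisson SE is sqrt(1/100 + 1/280) = 0.1165.
- ln(0.28/0.20) = 0.3365, and 0.3365/0.1165 - 1.96 = 0.93, which gives power 0.82.

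That is a separate matter and nothing below depends on it.

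**Which offset the plan implies.** 0.20/0.5 = 0.40 and 0.28/0.5 = 0.56, so the quoted rates give every subject the full half year. Stopping time at diagnosis under a constant hazard would give -ln(0.80)/0.5 = 0.446 and -ln(0.72)/0.5 = 0.657. Objective 1 was therefore planned on total time. For objective 2, 0.10/0.25 = 0.40, not the stated 0.25, so its rates do not settle the question.

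**Total time as offset, equal follow-up.** With x and y events in n1 and n2 subjects:
- log rate ratio = ln[(y/n2)/(x/n1)]
- Poisson SE = sqrt(1/x + 1/y)
- robust SE = sqrt(1/x - 1/n1 + 1/y - 1/n2)

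At 20% v 28% these are 0.1165 and sqrt(0.0100 - 0.0020 + 0.00357 - 0.0010) = 0.1028, a ratio of 1.13. Under the null the ratio is 1/sqrt(1-p): 1.12 at 20% and 1.34 at 44%. Summing rejection probabilities exactly over both binomials gives:

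| Setting | Poisson variance | Robust variance |
|---|---|---|
| Type I error, 20%, 500/1000 | 0.028 | 0.049 |
| Type I error, 44%, 500/1000 | 0.009 | 0.049 |
| Type I error, 10%, 100/200 | 0.032 | 0.040 |
| Power, 20% v 28%, 500/1000 | 0.87 | 0.92 |
| Power, 10% v 26%, 100/200 | 0.88 | 0.92 |
| Power, 44% v 52%, 500/1000 | 0.57 | 0.83 |

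On rows of SAP Table 2, with 500 in Phase I and the tabled Phase II size, a normal approximation gives 0.86 v 0.94 at 30% v 40%, 0.70 v 0.93 at 50% v 60%, and 0.44 v 0.96 at 70% v 80%.

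**Unequal follow-up and the other offset.** This is a null simulation with 500/1000 subjects. Follow-up is uniform on 6 to 18 months in both phases, and the hazard is set to give the stated proportion at six months. The follow-up pattern and hazard shapes are assumptions, because the documents do not give them. The front-loaded hazard is Weibull with shape 0.4.

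| Offset and hazard | Type I error, Poisson | Type I error, robust |
|---|---|---|
| Total time, constant, 20% | 0.013 | 0.047 |
| Total time, front-loaded, 44% | 0.005 | 0.052 |
| Stopped at event, constant, 20% | about 0.05 | about 0.05 |
| Stopped at event, front-loaded, 20% | about 0.07 | about 0.05 |
| Stopped at event, front-loaded, 44% | 0.105 | about 0.05 |

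**The case against.** **The offset decides the direction.** If time stops at diagnosis or implant, the Poisson model is the exponential time-to-event likelihood, and its standard errors are right under a constant hazard. This stands. A reader might infer that the Poisson standard errors are always too large and the tests always conservative. The documents do not support that, because the end of time in study is undefined and the exit rules in Protocol 5.7 tie it partly to the outcome. With a front-loaded hazard and time stopped at the event, the default errs the other way.

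**The size.** A reader might infer that the tests lose much of their power as planned. They do not: the loss is about 5 points for objective 1 and 4 for objective 2. The large losses belong to event proportions near or above 40 to 50%. Those are in the SAP's scenario tables, and 44% is the only prior SND figure cited, but they are not the design assumption.

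**The redaction.** A reader might infer that the SAP has chosen the Poisson variance. That cannot be shown. The hidden text in 8.5.1.1 may hold code that names a variance; the SAP's version history mentions SAS code. The model descriptions in 8.2.1 and 8.5.2.1 show no redaction and name none.

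**The role of these models.** They are additional to the chi-square and Fisher tests, which are unaffected. SAP 8.4 names only the two proportions as primary endpoints, SAP 4.1 calls the study exploratory, and log-rank tests also compare timing. This limits the consequence. It does not make a wrong interval right, and the beta1 test has no readable substitute.

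**Conclusion.** The concern holds in a conditional form. The default Poisson variance is generally not valid for these yes/no outcomes, and the readable plan names no alternative.

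- **Total time as offset** (the reading the objective 1 rates support): standard errors are too large by about 1/sqrt(1-p). Type I error is 0.028 at 20% and 0.009 at 44%. The power loss is about 4 to 5 points at the planned rates and 26 points at 44% v 52% (0.83 - 0.57).
- **Time stopped at the event:** standard errors are correct under a constant hazard and too small under a front-loaded one, with type I error up to about 0.10.

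The first result assumes equal follow-up and two-sided 0.05; the second rests on the simulated follow-up and hazard shapes above. The comparisons of proportions stand as planned. The change is worth making because the robust variance holds close to nominal size under either offset, at almost no cost.

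**What to change.** Keep the Poisson models in SAP 8.5.1.1, 8.5.2.1 and 8.2.1. Add two statements:

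1. All tests and 95% confidence intervals from these models, including those for beta1 and beta2, use the robust (sandwich) subject-level variance.
2. Time in study for the offset ends at a defined point for each objective: either at the event or at the end of follow-up.

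The cost is a short SAP amendment, one option in the regression code, and an offset computed to match. No data or design change is needed. If the redacted text already names a robust variance for objective 1, carry it to the other two models. The one drawback is that with very few events (about 10 Phase I implants) the robust test is slightly conservative, with size 0.040. That is still closer to 0.05 than the model-based 0.032.
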